¹Pre-study assessments need to be completed within 14 days prior to randomization. Day 1 must occur within 5 calendar days of randomization.

²Subjects who discontinue during the On-therapy Period in the absence of progressive disease will enter the Off-therapy Observation Period of the study (see schedule below). If at any time a subject initiates a non-protocol therapy, the subject will be removed from study and treated as per individual investigator discretion.

³In addition to the end of each month visit assessments. Window for all visits is during treatment is ± 2 days. Window for laboratory assessments before study visits is -7 days.

⁴Complete these assessments if a subject develops PSA or radiographic progression before the end of Month 12. The subject will then be removed from study and treated as per individual investigator discretion

⁵Choice of LHRHa is per investigator's discretion. The first dose of ARN-509 or LHRHa will be on Day 1. ARN-509 will be administered daily with or without food. All subjects should be following a 28-day, 28-day, 35-day schedule for their monthly visit (i.e., the 1st post-Day 1 visit is scheduled for 28 days later, the 2nd post-Day 1 visit is scheduled for 28+28 days later, the 3rd post-Day 1 visit is scheduled for 28+28+35 days later, the 4th post-Day 1 visit is scheduled for 28+28+35+28 days later, etc). If a subject does not receive a scheduled LHRHa injection within ± 7 days of the scheduled due date for injection, he will be removed from study

⁶Physical exam changes will not be collected in the eCRF, any change in physical exam from baseline needs to be recorded on the adverse event page

⁷Adverse event collection starts from signing the ICF. For subjects who discontinue therapy and do not proceed to the Off-therapy Period, AEs must be recorded up to 30 days after the last dose of study medication.

⁸See Section 7.5.4.

⁹Scans need to be done within 6 weeks prior to randomization. At the Progression Visit, scans may be omitted if already done within the prior 1 month.

¹⁰At the Progression Visit, may be omitted if already done with the prior 1 month.

¹¹For reference, see, <https://www.shef.ac.uk/FRAX/tool.aspx?country=9>. DEXA scan is also to be used for osteoporosis assessment.

¹²DEXA scan needs to be done within 12 weeks prior to randomization. At Progression Visit, scans may be omitted if already done within the prior 1 month.

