11.4.2 Analytic Plan for the Secondary Endpoints

The secondary QOL endpoints will be analyzed using a similar approach as for the primary endpoint. Data up to 24 months will be included in the analysis.

PSA Modulation:

The proportion of subjects without PSA or radiographic progression and who have recovered serum testosterone to greater than 150 ng/dL at 24 months from Day 1 will be compared for subjects treated ARN-509 monotherapy vs. LHRHa monotherapy and for ARN-509 + LHRHa vs. LHRHa monotherapy. The proportions by treatment will be compared using the chi-square test or Fisher's exact test as appropriate. Results will be summarized at 24 months from Day 1 with 95% confidence intervals for each treatment arm. Subjects who withdraw from the study prior to 24 months after Day 1 will not be included in this analysis. Details can be found in the statistical analysis plan (SAP).

The proportion of subjects with a PSA less than 0.2 ng/mL after 7 months of protocol therapy will be analyzed using similar approaches for proportion of subjects without evidence of PSA or

radiographic progression during the 24-month treatment period and with recovery of serum testosterone at 24 months.

The probability distributions by treatment group of the time to PSA progression will be estimated using the Kaplan-Meier method. Durations will be measured from Day 1 of study treatment to the first date of PSA progression. The log-rank test will be used to compare the distribution of time to PSA progression.

Metabolic and Hormonal Parameters:

The mean change from baseline for markers of insulin resistance (including fasting glucose, insulin, body mass index, and hemoglobin A1C), fasting lipid panel (including total cholesterol, LDL, HDL, and serum triglycerides), and hormone levels (including DHT and estradiol) analyzed using a similar approach as for the primary endpoint.

The mean change in bone mineral density at the femoral neck, and lumbar spine as measured by DEXA scan will be compared for ARN-509 monotherapy vs. LHRHa monotherapy and ARN-509 + LHRHa vs. LHRHa monotherapy using an analysis of covariance (ANCOVA) that controls for baseline values of the corresponding measurement.

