1.2 Trial Design

This is a randomized, multicenter, open-label, 3-arm phase 2 clinical trial evaluating 12 months of treatment with luteinizing hormone releasing hormone agonist (LHRHa) monotherapy, apalutamide monotherapy, or the combination of apalutamide and LHRHa, in men with non-metastatic BCR prostate cancer with rapidly rising PSA levels after prior definitive therapy for localized prostate cancer. Enrollment of approximately 90 subjects (30 per arm) is planned for this study. Patients will be followed for safety and efficacy as per the schedule of assessments and will remain on study treatment until the time of PSA or radiographic progression or initiation of non-protocol therapy or subject/physician withdrawal from the study, whichever occurs first. Subjects will be stratified by PSADT (< 6 months vs. 6-12 months) and age (≤ 70 vs. > 70). There will be 2 periods of 12 months each in the 24-month-long treatment period: 1) an on-

therapy period lasting 12 months, during which time subjects receive randomly assigned protocol therapy, and 2) an off-therapy observation period also lasting 12 months. If there is no evidence of PSA or radiographic progression after 24 months from Day 1 of the on-treatment period, subjects will enter a follow-up period. Subjects will remain on study until the time of PSA or radiographic progression or initiation of non-protocol therapy or subject/physician withdrawal from the study, whichever occurs first. Patients who discontinue before completion of the on-therapy period in the absence of progressive disease will enter the off-therapy observation period of the study.

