2.1 Analysis Sets

The following analysis sets will be used for this study:

Intent-to-Treat (ITT) Population: The ITT population includes all randomized subjects and will be classified according to their assigned treatment group, regardless of the actual treatment received. Subject disposition and efficacy analyses will be performed on data from the ITT population.

Safety Population: The safety population includes all subjects who received at least 1 dose of study drug as actually treated.

Modified Intent-to-Treat Population (mITT): For outcomes related to testosterone recovery, subjects who withdrew from the study prior to 24 months after day 1 will be excluded from the analysis.

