4.2 Disposition Information

Subject enrollment and disposition will be summarized by treatment group. The summary of subject disposition will display the number of subjects randomized, and the numbers of subjects

in ITT, safety. The summary will also include the number and percent of subjects who completed the study and who discontinued from the study and study treatment, respectively, and reason for discontinuation as documented in the subject status case report form.

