5.3 Secondary Endpoints

The following secondary endpoints will be analyzed:

A) Quality of Life:

- Mean change from baseline in total FACT-P score over time
- Mean change from baseline in EORTC QLQ-C30/PR25 score over time
- Mean change from baseline in SHIM score over time

B) PSA Modulation:

- Time to PSA progression, which is defined as a rise to greater than 50% of the baseline serum PSA or rise of 2 ng/mL or more above the nadir, whichever is higher, confirmed by repeat measurement at least 2 weeks later (see Table 1 for the censoring rules).
- Proportion of subjects without evidence of PSA or radiographic progression during the 24-month treatment period and with recovery of serum testosterone at 24 months. Testosterone recovery will be defined as a serum testosterone greater than 150 ng/dL.
- Proportion of subjects with a PSA less than 0.2 ng/mL after 7 months of protocol therapy

C) *Metabolic and Hormonal*

- Mean change from baseline in markers of insulin resistance (including body mass index, fasting glucose/insulin, and hemoglobin A1C), fasting lipid profile, and bone mineral density as measured at the femoral neck, and lumbar spine by DEXA scan over time
- Time to testosterone recovery to greater than 50 ng/dL (non-castrate) and greater than 150 ng/dL during the off-therapy observation period for subjects randomized to the LHRHa-based treatment arms (see Table 1 for the censoring rules)
- The mean change from baseline in serum DHT and estradiol levels over time

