5.3.1.2 PSA Modulation

The proportion of subjects without PSA or radiographic progression and who have recovered serum testosterone to greater than 150 ng/dL at 24 months from Day 1 will be compared for subjects treated apalutamide monotherapy vs. LHRHa monotherapy and for apalutamide + LHRHa vs. LHRHa monotherapy. The proportions by treatment will be compared using the chi-square test or Fisher's exact test as appropriate and summarized using either risk ratio or risk difference and corresponding 95% confidence interval. Results will be summarized at 24 months from Day 1 with 95% confidence intervals for each treatment arm. Subjects who withdraw from the study prior to 24 months after Day 1 will not be included and this analysis will be conducted as modified intent-to-treat (mITT).

The proportion of subjects with a PSA less than 0.2 ng/mL after 7 months of protocol therapy will be analyzed using similar approaches for proportion of subjects without evidence of PSA or radiographic progression during the 24-month treatment period and with recovery of serum testosterone at 24 months.

The probability distributions by treatment group of the time to PSA progression will be estimated using the Kaplan-Meier method. Durations will be measured from Day 1 of study treatment to the first date of PSA progression. The log-rank test will be used to compare the distribution of time to PSA progression.

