5.3.1.3 Metabolic and Hormonal Parameters

The mean change from baseline for markers of insulin resistance (including fasting glucose, insulin, body mass index, and hemoglobin A1C), fasting lipid panel (including total cholesterol, LDL, HDL, and serum triglycerides), and hormone levels (including DHT and estradiol) analyzed using a similar approach as for the primary endpoint.

The mean change in bone mineral density at the femoral neck, and lumbar spine as measured by DEXA scan will be compared for apalutamide monotherapy vs. LHRHa monotherapy and apalutamide + LHRHa vs. LHRHa monotherapy using an analysis of covariance that controls for baseline values of the corresponding measurement.

The time to serum testosterone recovery to > 50 ng/dL and > 150 ng/dL after the cessation of protocol therapy at 12 months will be compared for apalutamide + LHRHa vs. LHRHa monotherapy. The probability distributions by treatment group of the time to testosterone recovery will be estimated using the Kaplan-Meier method. The log-rank test will be used to compare the distribution of time to testosterone recovery. Subjects who discontinue study drug prior to 12 months for disease progression, unacceptable toxicity, or study withdrawal, as well as subjects who continue hormonal therapy after 12 months or receive non-protocol therapy, will not be included in the analysis of this exploratory endpoint.

No adjustment for multiple comparisons will be made for the analysis of the secondary and correlative endpoints.

Table 1: Key censoring rules

Scenario	Censoring rule
Time to PSA Progression	
 Any increase in PSA to $> 50\%$ of the baseline value or an increase of ≥ 2 ng/mL above the nadir, whichever is higher, and confirmed by repeat measurement at least 2 weeks later is considered an event. Subjects who have no PSA progression at the time of analysis will be censored at the last known date of PSA assessment. Subjects without a baseline PSA or without any post baseline values will be censored at randomization date.

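### The exploratory 24-month proportion (progression-free with testosterone above 150 ng/dL) is planned only after dropping men who withdraw; an all-randomised companion and a definition of withdrawal should be added

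*SAP*

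**What the plan says.** **Endpoint.** SAP 5.3 lists "Proportion of subjects without evidence of PSA or radiographic progression during the 24-month treatment period and with recovery of serum testosterone at 24 months", with recovery set at more than 150 ng/dL. Protocol 6.4.2.3 calls it an exploratory secondary endpoint.

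**Exclusion.** SAP 5.3.1.2: "Subjects who withdraw from the study prior to 24 months after Day 1 will not be included and this analysis will be conducted as" mITT. Protocol 11.4.2 has the same rule: "Subjects who withdraw from the study prior to 24 months after Day 1 will not be included in this analysis". SAP 2.1 defines the mITT set for testosterone-recovery outcomes: "subjects who withdrew from the study prior to 24 months after day 1 will be excluded from the analysis".

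**General rule.** Protocol 11.3 assigns PSA-suppression endpoints to the ITT population, and SAP 5 does the same for efficacy analyses.

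**Ways of leaving.** SAP 1.2 keeps men on study until "PSA or radiographic progression or initiation of non-protocol therapy or subject/physician withdrawal from the study, whichever occurs first". For a different endpoint, time to testosterone recovery, SAP 5.3.1.3 names "Subjects who discontinue study drug prior to 12 months for disease progression, unacceptable toxicity, or study withdrawal" as separate reasons. Protocol 7.1, footnote 2: "If at any time a subject initiates a non-protocol therapy, the subject will be removed from study". Protocol 7.5.2 and SAP 2.2.2 also remove a man whose LHRHa injection falls outside a 7-day window either side of the due date.

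**Missing data and displays.** SAP 5.1.2 plans no imputation in general. It leaves sensitivity analyses optional and frames them as censoring rules. The SAP 4.2 disposition table gives numbers of subjects "in ITT, safety. The summary will also include the number and percent of subjects who completed the study" or discontinued, with reasons. The mITT set is not among the sets it lists.

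**The concern.** Randomisation protects a comparison of everyone randomised. It does not protect a comparison of those who happen to remain at Month 24. Treatment is open-label, so a man's decision to leave, or his physician's, can depend on the arm he was given. Dropping such men raises the proportion in each arm and can move the arm difference in either direction. The plan has no all-randomised result to set beside the restricted one.

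The exclusion also turns on one undefined word. Where an exit does not plainly fall inside or outside *withdraw*, it could be classified after the data have been seen. One such exit, removal for a missed LHRHa injection, can occur only in the two LHRHa-containing arms. It is therefore one-sided in the comparison of apalutamide monotherapy with LHRHa.

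What is at stake is the reading of a hypothesis-generating result. Hypothesis 2 names durable PSA suppression coupled with testosterone recovery among the findings that would support larger trials, and this endpoint combines the two.

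**Working it through.** **1. What *withdraw* covers.** SAP 1.2 lists subject/physician withdrawal separately from progression and from non-protocol therapy. SAP 5.3.1.3 lists study withdrawal separately from disease progression and unacceptable toxicity. The consistent reading is subject/physician withdrawal only. Each exit then falls as follows:

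| Exit or gap | Handling for this endpoint |
|---|---|
| PSA or radiographic progression | In the denominator; a failure by the endpoint definition |
| Non-protocol therapy without progression | In the denominator; not a withdrawal |
| Drug stopped early without progression | Not an exit; enters the off-therapy period (protocol 3.1, SAP 1.2) |
| Subject/physician withdrawal before Month 24 | Excluded |
| Removal for a missed LHRHa injection | Not stated; absent from the SAP 1.2 list |
| On study, no Month-24 testosterone | Not stated; no imputation (SAP 5.1.2) |

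SAP Table 1 does not settle the last two rows, because it covers only the two time-to-event endpoints.

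**2. Figures in the plan.** No expected rate, power or Month-24 withdrawal rate is given for this proportion. The only attrition figure is 10% for FACT-P (protocol 11.1, SAP 1.4): 30 × 0.90 = 27, as stated. It is borrowed below only to set a scale.

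**3. Effect of the exclusion on one arm.** With *r* successes, *N* = 30 and *w* withdrawals, the mITT proportion is r/(30 − w), against r/30 for all randomised. The ratio is 30/(30 − w): 1.11 for w = 3 and 1.25 for w = 6.

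**4. Effect on the difference.** All counts are assumed: 8 successes in control, 14 in the experimental arm, and withdrawals of 3 or 6. No withdrawn man has a Month-24 result, so the success counts do not change. Intervals are Newcombe 95% intervals, built from the Wilson limits (l, u) of each proportion p, with 1 = control, 2 = experimental and d = p2 − p1:

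lower = d − √[(p2 − l2)² + (u1 − p1)²]; upper = d + √[(u2 − p2)² + (p1 − l1)²].

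For all randomised, the Wilson limits are 0.142 to 0.444 for 8/30 and 0.302 to 0.639 for 14/30. The lower limit is 0.200 − √(0.164² + 0.178²) = −0.042. The upper limit is 0.200 + √(0.172² + 0.125²) = 0.412.

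| Denominator | Control | Experimental | Difference, points (95% CI) | Shift |
|---|---|---|---|---|
| All randomised | 8/30 = 26.7% | 14/30 = 46.7% | 20.0 (−4.2 to 41.2) | – |
| 3 and 3 excluded | 8/27 = 29.6% | 14/27 = 51.9% | 22.2 (−3.8 to 44.4) | +2.2 |
| 6 and 6 excluded | 8/24 = 33.3% | 14/24 = 58.3% | 25.0 (−2.9 to 48.1) | +5.0 |
| 6 and 3 excluded | 8/24 = 33.3% | 14/27 = 51.9% | 18.5 (−8.3 to 41.7) | −1.5 |
| 3 and 6 excluded | 8/27 = 29.6% | 14/24 = 58.3% | 28.7 (1.6 to 50.7) | +8.7 |

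The half-width of the all-randomised interval is (41.2 + 4.2)/2 = 22.7 points, so every shift is well inside it.

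**5. The missed-injection gap.** Start from 3 withdrawals per arm (22.2 points), comparing apalutamide monotherapy with LHRHa. Suppose 1, 2 or 3 men in the LHRHa arm were removed for a missed injection and are counted as withdrawals. The control proportion becomes 8/26, 8/25 or 8/24, and the difference 21.1, 19.9 or 18.5 points. If they stay in the denominator it remains 22.2.

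**6. The companion can shift too.** Take 12/24 versus 14/28: 50.0% in each arm, 0 points. With all 30 per arm as denominators this becomes 12/30 = 40.0% versus 14/30 = 46.7%, or 6.7 points. The movement comes from unequal exits (6 versus 2) being scored as non-successes.

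**The case against.** The strongest defence is that the population was declared. Three sections state the same exclusion and the SAP names the set. A specific rule overrides a general default, so a reader who infers a hidden contradiction with ITT is not supported by the text.

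Much of the missing result can also be recovered. SAP 5 requires counts and percentages for binary endpoints, and SAP 4.2 reports numbers randomised and reasons for discontinuation. Successes divided by number randomised is the all-randomised proportion. Both points stand. What remains is that this comparison is not pre-specified, and that two situations have no rule.

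A reader might go further in four ways, none of which the documents support:

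- **Progressors are dropped, which inflates success.** They leave the study, but the lists in SAP 1.2 and 5.3.1.3 keep progression apart from withdrawal, and the endpoint definition counts progressors as failures.
- **Non-protocol-therapy removals are unclassified.** On the same reading they are not withdrawals, so they stay in the denominator.
- **The Month-24 exclusion carries over to PSA below 0.2 ng/mL at Month 7.** SAP 5.3.1.2 refers to similar approaches for that endpoint, but SAP 2.1 confines the mITT set to testosterone-recovery outcomes.
- **The all-randomised analysis should replace the mITT analysis.** Scoring every exit as a non-success is itself an assumption, and step 6 shows it producing a difference. Missed-injection removals would count only against LHRHa-containing arms. This is a trade-off between two imperfect conventions, so the case is for showing both.

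**Conclusion.** The point holds as a minor one. The 24-month proportion is planned only on a denominator formed after randomisation in an open-label trial. It has no all-randomised companion, and two situations have no stated handling.

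The size cannot be established from the documents. In the illustration the difference ranges from 18.5 to 28.7 points against 20.0 for all randomised, a shift of −1.5 to +8.7. This rests entirely on assumed success counts (8 and 14 of 30) and assumed withdrawals (3 or 6 per arm). One interval in that table excludes zero, and a reader might conclude that the exclusion can manufacture a positive finding. The assumed counts do not support that: the shift is under half the 22.7-point half-width, and it needs twice as many withdrawals in the experimental arm as in control.

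Consequences are limited. The endpoint is exploratory and unpowered, and secondary endpoints carry no multiplicity adjustment. Time to PSA progression is analysed separately, and the primary FACT-P analysis is unaffected.

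**What to change.** Keep the pre-specified mITT analysis and make these changes:

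1. In SAP 5.3.1.2, add a companion analysis with all randomised subjects as denominator (30 per arm as planned). Success is documented progression-free status through Month 24 plus a Month-24 testosterone above 150 ng/dL. Everyone else is a non-success.
2. In SAP 2.1 and 5.3.1.2 and protocol 11.4.2, limit *withdraw* to subject/physician withdrawal.
3. Before database lock, state how the mITT analysis treats a man removed for a missed LHRHa injection and a man on study without a Month-24 testosterone.
4. Report the mITT size and the exclusions by arm, with reasons, in the SAP 4.2 disposition summary.

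The cost is wording and one extra table line; no new data are needed. The companion proportions will be lower: with 3 withdrawals per arm in the illustration, 29.6% becomes 26.7% in control and 51.9% becomes 46.7% in the experimental arm. Unequal exits can shift the companion difference as well, so the two analyses should be shown side by side.

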6.4.2.3 PSA Modulation and Hormone Levels

The extent to which a therapeutic intervention modulates PSA levels has not been extensively evaluated as an intermediate marker of outcome in patients with BCR prostate cancer. In the proposed trial, three different aspects of PSA modulation will be evaluated: PSA nadir level, time to PSA progression, and PSA non-progression in the face of normal testosterone levels. In addition, the effect of the therapeutic interventions on relevant hormonal levels such as testosterone, DHT and estradiol will be evaluated.

PSA Nadir: In a prior clinical trial of men with metastatic hormone sensitive prostate cancer, after 7 months of induction ADT, men with a nadir PSA level of less than 0.2 ng/mL vs. 0.2 thru 4.0 vs. > 4.0 had a progressively shorter overall survival, declining from a median of 75 to 44 to 13 months, respectively [52]. Further, recommendations for trial design in BCR disease by the PSA Working Group [50] suggest that PSA decline can form the basis for larger trials using primary endpoints such as metastasis-free or overall survival. Whether the PSA nadir data observed in patients with metastatic disease is relevant to patients with BCR is not known. Nevertheless, as an exploratory secondary endpoint, the proportion of men achieving a PSA nadir after 7 months of protocol therapy of less than 0.2 ng/mL will be measured in the proposed trial. Validation of nadir PSA as a potential intermediate endpoint of metastasis-free or overall survival, however, will require confirmation in large prospective trials in this disease setting.

Time to PSA Progression: There is no consensus or standardized definition of PSA progression in the BCR disease setting. Various PSA thresholds have been used as a “trigger” to initiate treatment in prior trials of IADT, ranging from < 1.0 ng/mL to 20 ng/mL [47]. The recently reported NCIC-PR7 international trial of continuous vs. intermittent ADT used a PSA threshold of 10 ng/mL to restart ADT in the intermittent treatment arm [26], although this relatively high PSA value would be unlikely to be accepted by patients in the United States, who are accustomed to taking action based on much lower PSA values.

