7.5.7 Laboratory Assessments

Subjects who experience disease progression (PSA or radiographically) before the end of 12 months should complete laboratory assessments at the Progression Visit as outlined in the Study Schedule. During treatment, laboratory assessments include the following:

- Serum PSA level measured by ultrasensitive assay at the end of each month
- Complete blood count including differential and platelet count at the end of Months 3, 6, 9, and 12 of protocol therapy.
- Total bilirubin, alkaline phosphatase, AST, ALT at the end of Months 3, 6, 9, and 12.
- TSH at the end of Months 3, 6, 9, and 12.
- Fasting glucose, fasting lipid panel (total cholesterol, LDL, HDL, triglyceride), and hemoglobin A1C at the end of Months 3, 6, 9, and 12.
- Peripheral blood collection for measurement of serum testosterone, DHT, estradiol, and fasting serum insulin levels at the end of Months 3, 6, 9, and 12 (see Appendix 6 for collection, processing, and shipping instructions).
- Peripheral blood and urine collection for banking of, serum, plasma, and urine at the end of Months 3, 6, 9, and 12 of protocol therapy (optional). See Appendix 6 for procedures to ensure subject confidentiality and instructions on collection, processing, shipping of samples.
- Whole blood collected for PAXgene analysis (optional) on Day 1 and end of Month 12

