1.3 Statistical Hypotheses for Trial Objectives

1.3.1 Hypothesis 1

For men with non-metastatic, non-castrate prostate cancer who have rapidly rising PSA levels after definitive local therapy, treatment with 12 months of apalutamide monotherapy compared with 12 months of ADT in the form of LHRHa monotherapy will result in better preservation of QOL as measured by the FACT-P scale. Parallel and exploratory findings demonstrating comparable PSA suppression, and less negative impact on the metabolic profile (including measurements of fasting lipid profiles, insulin resistance, and bone mineral density) of subjects who receive apalutamide monotherapy as opposed to therapy with an LHRHa would form the preliminary basis for further definitive study of apalutamide monotherapy in biochemically relapsed prostate cancer.

1.3.2 Hypothesis 2

For men with non-metastatic, non-castrate prostate cancer who have rapidly rising PSA levels after definitive local therapy, treatment with 12 months of therapy with the combination of apalutamide + LHRHa, compared with 12 months of therapy with LHRHa alone, will not be associated with a clinically significant worsening of QOL as measured by the FACT-P scale. Parallel, exploratory findings suggesting more durable PSA suppression coupled with adequate serum testosterone recovery, favorable PSA modulation with respect to PSA nadir and time to PSA progression, along with acceptable safety data, would form the preliminary basis for larger clinical trials testing the combination of apalutamide plus LHRHa vs. LHRHa alone in the hormone sensitive prostate cancer disease setting.

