5. EFFICACY

This section outlines the planned analyses of the primary, secondary, and other efficacy endpoints of the study.

Efficacy analyses will be performed in the ITT population, incorporating the randomization stratification factors. All continuous variables will be summarized using number of subjects (n), mean, standard deviation (SD), median, minimum, and maximum. Categorical variables will be summarized with count and percentage.

Time-to-event endpoints will be summarized using the Kaplan-Meier method [6] and displayed graphically where appropriate. Median event times and two-sided 95% confidence interval (CI) for each treatment group will be provided. Stratified Cox proportional-hazard models will be used to estimate the hazard ratio (HR) and its 95% CI. The stratification factors to be used in the analysis are PSADT (< 6 months vs. 6-12 months), and age at study entry (≤ 70 years vs. > 70 years).

The testing for the time-to-event endpoints will be based on the stratified log rank test; non-stratified log rank test will be performed as a sensitivity analysis, as appropriate. Multivariate Cox regression analysis, adjusting for important selected prognostic factors.

The proportional hazard assumption will be assessed graphically by plotting log (-log [estimated survival distribution function]) against log (survival time). The resulting graphs should have approximately parallel lines when the assumption holds. If the proportional hazards assumption is reasonably met, then the HR will be used as an estimate of treatment effect. If the proportional hazards assumption is violated, then the inference remains statistically valid for testing equality in survival distributions, but treatment effect will only be estimated using the median time to event in each treatment group.

Endpoints with binary outcome will be summarized by descriptive statistics (count and percentage) by the treatment group. The risk ratio or risk difference (treatment: control) will be reported along with the corresponding two-sided 95% CI. The two treatment groups will be compared by using the chi-square test; Fisher's exact test may be used if the expected counts in some of the cells are less than 5.

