5.1 Analysis Specification

5.1.1 Level of Significance

In general, a two-sided significance level of $\alpha = 0.05$ will be used for all hypothesis testing and all CIs will be calculated on the two-sided 95% confidence level, unless otherwise specified. Since this is a three-arm study testing two simultaneous hypotheses, $\alpha/2 = 0.025$ level of significance will be used to test each.

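### Month-7 PSA is compared between arms only as below 0.2 ng/mL or not; a supplementary comparison on the PSA scale would keep the information on depth of suppression

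*SAP*

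**What the plan says.** The endpoint in SAP 5.3 is "Proportion of subjects with a PSA less than 0.2 ng/mL after 7 months of protocol therapy". SAP 5.3.1.2 sets the analysis: "The proportion of subjects with a PSA less than 0.2 ng/mL after 7 months of protocol therapy will be analyzed using similar approaches" to those for the 24-month composite. For that composite, "The proportions by treatment will be compared using the chi-square test or Fisher's exact test as appropriate", with a risk ratio or risk difference and its 95% CI. SAP 5 adds that "Fisher's exact test may be used if the expected counts in some of the cells are less than 5". By SAP 5.1.1 a two-sided 0.05 level "will be used for all hypothesis testing and all CIs will be calculated on the two-sided 95% confidence level" unless otherwise specified, and SAP 5.3.1.3 makes no multiplicity adjustment for secondary endpoints.

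The underlying measurement is continuous. Protocol 7.5.7 lists "Serum PSA level measured by ultrasensitive assay at the end of each month". Protocol 10.6 places the assay at local laboratories and only prefers the same laboratory for each man. Protocol 7.3 makes the Day 1 value the PSA baseline.

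Protocol 6.4.2.3 explains the cut. In a trial in metastatic disease, men with a 7-month PSA below 0.2, from 0.2 to 4.0 and above 4.0 ng/mL had median survival of 75, 44 and 13 months. The same section concedes: "Whether the PSA nadir data observed in patients with metastatic disease is relevant to patients with BCR is not known". It calls the endpoint exploratory.

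**The concern.** Hypothesis 1 (SAP 1.3.1) looks to "Parallel and exploratory findings demonstrating comparable PSA suppression" as part of the basis for further study of monotherapy. Hypothesis 2 (SAP 1.3.2) names PSA nadir among the findings that would support larger trials of the combination. Both concern depth of suppression on therapy, and the single yes/no cut at 0.2 ng/mL is the only planned between-arm comparison that addresses it. Time to PSA progression measures durability.

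The metabolic and hormonal markers, by contrast, are compared on their own scales with a repeated-measures model (SAP 5.3.1.3).

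If most men in every arm fall below 0.2 ng/mL, which is plausible in low-burden hormone-sensitive disease, the binary comparison meets a ceiling. Two arms could differ in depth of suppression and the planned test would have almost no chance of showing it.

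**Working it through.** **The plan's own figures.** Neither document states a power, expected rate or SD for Month-7 PSA. The only power figure nearby is for the primary FACT-P superiority test: 27 per arm, difference 7.5, SD 8.7, two-sided 0.025. The noncentrality is (7.5/8.7) × √(27/2) = 3.17 on 52 degrees of freedom, giving 80.2% against the stated 80%. It reproduces but does not bear on this endpoint.

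**Inputs from the documents.** 30 men per arm (SAP 1.4); two-sided 0.05; chi-square, with Fisher when an expected count is below 5.

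**Inputs assumed.** The control rate below 0.2, the size and form of the treatment effect, and the assay floor.

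**Model A: treatment shifts log PSA.** Take log PSA as normal with SD 1 in each arm and control rate p0. The cut is c = Φ⁻¹(p0), and a shift of d gives an experimental rate p1 = Φ(c + d). For p0 = 70% and d = 0.75: c = 0.524 and p1 = Φ(1.274) = 90%. The planned rule is compared with a tie-corrected Wilcoxon test, with all values below a floor 0.7 SD under the cut tied.

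| Control v other arm below 0.2 (0.75 SD shift) | Planned test | Wilcoxon |
|---|---|---|
| 50% v 77% | 60% | 75% |
| 70% v 90% | 45% | 68% |
| 80% v 94% | 26% | 64% |
| 90% v 98% | 4% | 48% |
| 70% v 41% (other arm worse) | 63% | 76% |
| 80% v 54% (other arm worse) | 59% | 75% |

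At a 0.5 SD shift the gain is about 10 to 25 points. Over both shifts and control rates of 50% to 90%, it is about 10 to 46 points. Wilcoxon type I error stays at about 4% to 5%.

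**Effect of the floor.** If every value below 0.2 is tied, the gain falls to about 1 to 19 points. At 0.75 SD and control rates of 50% to 70%, raising the floor from 0.7 SD below the cut to the cut itself takes the gain from 15–22 points to about 5.

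**Why the ceiling bites.** At 90% v 98%, the expected number of men not below 0.2 is 30 × 0.10 = 3 in control and 30 × 0.02 = 0.6 in the other arm. The expected counts are therefore below 5 and Fisher applies. Five such men v none gives p = 2 × C(30,5)/C(60,5) = 2 × 142,506/5,461,512 = 0.052. Six v none gives 2 × 593,775/50,063,860 = 0.024. Even with none in the better arm, significance needs six in control, twice the expected number. Power at a 90% control rate is about 3% for a 0.5 SD improvement and 4% to 5% for 0.75 SD.

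**Model B: treatment changes only the fraction of deep suppressors.** Two groups are centred 1.5 units either side of the cut (SD 0.7), with a floor 0.7 units below the cut.

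| Deep suppressors, control v other arm | Planned test | Wilcoxon |
|---|---|---|
| 50% v 80% | 66% | 60% |
| 60% v 85% | 55% | 50% |
| 70% v 92% | 52% | 46% |
| 70% v 40% | 62% | 56% |

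The planned test leads by about 4 to 7 points here, and by about 10 to 20 with no floor, because ranking within each group adds only noise.

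**Precision.** At 80% in both arms, the 95% CI half-width for the difference is 1.96 × √(2 × 0.8 × 0.2/30) = 0.202, or about 20 points.

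**The case against.** The endpoint is a proportion, and chi-square or Fisher is a valid test of it. The cut has a stated clinical anchor that a ratio of geometric means lacks, and the protocol claims no power for this exploratory endpoint. All of that stands, and it is why the proportion and its test should stay.

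Four stronger readings are tempting and should not be drawn.

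- **That the plan loses a fixed amount of power, say 10 to 40 points.** The documents supply none of the inputs such a figure needs. The gain under Model A ranges from about 1 point to more than 40, depending on the floor and the control rate, and Model B reverses the direction.
- **That the binary test should be replaced.** The documents do not say which model is nearer the truth, so replacement is a trade-off.
- **That PSA is never summarised on its own scale.** SAP 6.1.1 plans by-visit descriptive statistics for local laboratory tests. It does not name PSA, but the wording could cover it. What is missing is a between-arm comparison.
- **That a non-significant test will be read as comparability.** Neither document says so. SAP 5 and 5.3.1.2 require a confidence interval, which would show imprecision of the order of 20 points. A non-significant rank test would not show comparability either.

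**Conclusion.** The point holds as a modest improvement. Month-7 PSA enters the between-arm analysis only through one cut, while depth of suppression is part of both hypotheses and the continuous values are already collected. The size of the loss is conditional on normal log PSA with equal SDs, a uniform shift, 30 evaluable men per arm and a floor well below 0.2 ng/mL. The most robust part is the ceiling: at a 90% control rate the planned test is close to powerless against a 0.5 to 0.75 SD improvement, and a rank test still gains if everything below 0.2 is tied (at 0.74 SD, 21% v 4%). The consequence is a weak exploratory comparison of activity. The primary FACT-P analysis is unaffected.

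**What to change.** In SAP 5.3.1.2, keep the proportion below 0.2 ng/mL with its planned test and 95% CI. Add one prespecified supplementary comparison of Month-7 PSA for each experimental arm against LHRHa:

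- a left-censored regression of log PSA on treatment, adjusted for Day 1 log PSA, reporting the ratio of geometric means with its 95% CI;
- in support, because the regression relies on roughly normal log PSA, a van Elteren or Wilcoxon test with values below one common floor tied lowest.

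State the floor and how it is chosen. Add that comparability of PSA suppression will be judged from the confidence intervals, not from a non-significant p-value.

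The cost is SAP wording and one table, with no new data or visits. There are two downsides. With local laboratories, the common floor must be the highest across sites, and a high floor shrinks the gain. It also adds one more unadjusted exploratory comparison, which should be labelled as such.
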